## 7 DOSING DELAYS/DOSE MODIFICATIONS

The administration of Hu5F9-G4 (magrolimab) (in the "single agent Safety Lead-In" and/or during cycles of the combination cycles with Hu5F9-G4 (magrolimab) and dinutuximab) will be modified according to the attribution (possibly, probably or definitely related) to either Hu5F9-G4 (magrolimab) or dinutuximab.

The National Cancer Institute (NCI) CTCAE Version 5.0 will be used to grade AEs. Patients enrolled in this study will be evaluated clinically and with standard laboratory tests before and at regular intervals during their participation in this study as specified in this section.

Patients will be evaluated for AEs (all grades), SAEs and AEs requiring study drug interruption or discontinuation at each study visit for the duration of their participation in the study.

The primary approach to mild AEs (Grades 1–2) is supportive and symptomatic care. The general approach to clinically significant and/or unacceptable toxicity (Grade 3 AEs) is holding study treatment until the toxicity resolves (≤ Grade 2) and then resume at one dose level lower, if clinically indicated. Supportive therapy must be administered per standard clinical practice. Consultation with the protocol PI and/or the PED-CITN Coordinating Center is required.

Adverse Event specific guidelines are provided below.

# 7.1 Dosage modification for Hu5F9-G4 (magrolimab)

Nausea	Management/Next Dose for Hu5F9-G4 (magrolimab)	
≤ Grade 1	No change in dose	
Grade 2	Hold until ≤ Grade 1. Resume at same dose level.	
Grade 3	Hold until < Grade 2. Resume at one dose level lower, if indicated.*	
Grade 4	Off protocol therapy	
*Patients requiring a delay of >2 weeks should go off protocol therapy.		
Recommended managen	nent: antiemetics	

Vomiting	Management/Next Dose for Hu5F9-G4 (magrolimab)	
≤ Grade 1	No change in dose	
Grade 2	Hold until ≤ Grade 1. Resume at same dose level.	
Grade 3	Hold until < Grade 2. Resume at one dose level lower, if indicated.*	
Grade 4	Off protocol therapy	
*Patients requiring a de	lay of >2 weeks should go off protocol therapy.	
Recommended manage	ement: antiemetics	

Diarrhea	Management/Next Dose for Hu5F9-G4 (magrolimab)
≤ Grade 1	No change in dose
Grade 2	Hold until ≤ Grade 1. Resume at same dose level.
Grade 3	Hold until < Grade 2. Resume at one dose level lower, if indicated.*
Grade 4	Off protocol therapy
*Patients requiring	g a delay of >2 weeks should go off protocol therapy.

Recommended management: Loperamide antidiarrheal therapy with dosage schedule: 4 mg at first onset, followed by 2 mg with each loose motion until diarrhea-free for 12 hours (maximum dosage: 16 mg/24 hours)

Adjunct anti-diarrheal therapy is permitted and should be recorded when used.

Neutropenia	Management/Next Dose for Hu5F9-G4 (magrolimab)	
≤ Grade 1	No change in dose	
Grade 2	No change in dose.	
Grade 3	No change in dose.	
Grade 4 Hold until $\leq$ Grade 2. Resume at same dose level.*		
*Patients requiring a de	lay of >2 weeks should go off protocol therapy.	

Thrombocytopenia Management/Next Dose for Hu5F9-G4 (magrolimab)		
≤ Grade 1	de 1 No change in dose	
Grade 2	No change in dose.	
Grade 3 Hold until ≤ Grade 2. Resume at same dose level. *		
Grade 4 Hold until ≤ Grade 2. Resume at one dose level lower, if indicated. *		
*Patients requiring a del	ay of >2 weeks should go off protocol therapy.	

Anemia	Management/Next Dose for Hu5F9-G4 (magrolimab)
≤ Grade 1	No change in dose
Grade 2	No change in dose
Grade 3 hemolytic anemia that is	

Anemia	Management/Next Dose for Hu5F9-G4 (magrolimab)
	First occurrence: Reduce by 1 dose level.  • If recurs after 1 dose level reduction: permanently discontinue unless patient is clinically benefitting.
Grade 4	First occurrence: permanently discontinue unless patient is clinically benefitting.

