## 3.3 Inclusion of Women and Minorities

NIH policy requires that women and members of minority groups and their subpopulations be included in all NIH-supported biomedical and behavioral research projects involving NIH-defined clinical research unless a clear and compelling rationale and justification establishes to the satisfaction of the funding Institute & Center (IC) Director that inclusion is inappropriate with respect to the health of the subjects or the purpose of the research. Exclusion under other circumstances must be designated by the Director, NIH, upon the recommendation of an IC Director based on a compelling rationale and justification. Cost is not an acceptable reason for exclusion except when the study would duplicate data from other sources. Women of childbearing potential should not be routinely excluded from participation in clinical research. Please see http://grants.nih.gov/grants/funding/phs398/phs398.pdf.

Females ages 2 to 35 years of age will be included in this study. Any other age is outside the scope of this study.

There is no discrimination for the inclusion and planned distribution of patients by gender, race, ethnicity for this study (see Section 9.3, Planned Enrollment Report).

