### 6.1.1.1 Safety Assessment During "single agent Safety Lead-In"

Patients aged ≥2 or < 18 years of age will be enrolled on the "single agent Safety Lead-In", and will receive a therapeutic dose of Hu5F9-G4 (magrolimab) (30 mg/kg IV) on Day 1 of weeks 2 and 3 for a 21-day "single agent Safety Lead-In" cycle (see **Figure 1** and **Figure 2**). An assessment for DLTs as defined in **Section 6.3** will be performed during and at the end of the 21-day "single agent Safety Lead-In".

Any patient who does not develop DLT during the "single agent Safety Lead-In" may proceed to Cycle 1 (combination therapy with Hu5F9-G4 (magrolimab) plus dinutuximab) and will be evaluable for safety assessment during and after Cycle 1. When dinutuximab is administered immediately after Hu5F9-G4 (magrolimab), redosing with acetaminophen and diphenhydramine is not necessary. The intravenous line should be flushed well between drug administrations.

Patient enrollment and start of treatment during the safety "single agent Safety Lead-In" assessment will be staggered by 7 days for each patient enrolled. Three patients will initially be enrolled at Dose Level 1 (30 mg/kg IV).

- If 0 of the initial 3 patients develops a DLT during the 21-day "single agent Safety Lead-In", the next phase of safety will be evaluated in Cycle 1 as outlined below (Section 6.1.1.2).
- If 1 of the initial 3 patients develops a DLT (Section 6.3) during the 21-day "single agent Safety Lead-In", then an additional 3 patients will be enrolled at Dose Level 1.
  - o If 0 of these 3 additional patients (totaling 1/6) develops a DLT during the 21-day "single agent Safety Lead-In", the study will continue to evaluate DLTs in Cycle 1 as outlined below (Section 6.1.1.2).
  - o If ≥1 of these 3 additional patients (totaling 2/6) develop a DLT, the dose of Hu5F9-G4 (magrolimab) will be de-escalated to Dose Level -1 (20 mg/kg) during weeks 2 and 3 in the next 3 patients. The safety of Dose Level -1 will be similarly evaluated in 3-6 patients.
- If ≥ 2 of the initial 3 patients develop a DLT during the 21-day "single agent Safety Lead-In", the dose of Hu5F9-G4 (magrolimab) will be de-escalated to Dose Level -1 (20 mg/kg) during weeks 2 and 3, in the next 3 patients. The safety of Dose Level -1 will be similarly evaluated in 3-6 patients.
- If ≥ 2 patients develop DLT during the "single agent Safety Lead-In" using Dose Level -1, enrollment will pause pending discussions with the sponsor, IRB and FDA.

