# 7.2 Hu5F9-G4 (Magrolimab) AE Management and Dose Interruption Guidelines

For detailed information regarding management of AEs associated with Hu5F9-G4 (magrolimab), please refer to the most current version of the Hu5F9-G4 (magrolimab) Investigator's Brochure.

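### Section 7.1 prints one fixed loperamide schedule for every patient in a trial open from age 2, while every other supportive drug with a printed dose is per kg

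*Combined protocol and SAP*

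**What the plan says.** The diarrhea table in section 7.1 carries the line "Recommended management: Loperamide antidiarrheal therapy with dosage schedule" and then gives the schedule: "4 mg at first onset, followed by 2 mg with each loose motion until diarrhea-free for 12 hours (maximum dosage: 16 mg/24 hours". The next line allows other antidiarrheals as an adjunct, so loperamide is the base therapy. The nausea and vomiting tables in the same section name only a drug class and print no dose.

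The population is mostly pediatric. Section 3.1.5 opens both arms at age 2, Arm A up to 18 and Arm B up to 35. Section 6.1.1.1 says of the lead-in: "Patients aged ≥2 or < 18 years of age will be enrolled on the" single-agent phase. Section 3.3 gives the overall range: "Females ages 2 to 35 years of age will be included in this study".

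Three further texts bear on how the loperamide line would be applied:

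- The opening of section 7 states "Supportive therapy must be administered per standard clinical practice" and then "Consultation with the protocol PI and/or the PED-CITN Coordinating Center is required". It ends with "Adverse Event specific guidelines are provided below", and the table in 7.1 is one of those guidelines.
- Section 7.2 refers the reader to the current Investigator's Brochure for detail on managing magrolimab adverse events.
- Section 6.2.1.4 prints weight-based doses for analgesics and premedication and repeatedly defers to institutional guidelines.

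**The concern.** A supportive-care dose printed in a pediatric protocol should suit the youngest patient who can enroll. This one does not vary with body size, and nothing next to it tells a site to adjust it. It is also the only supportive drug dose in the protocol written that way, which suggests an adult schedule was carried over.

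The table can come into use. Diarrhea is listed as a possible effect of magrolimab in section 10.1.1.1 and as a dinutuximab reaction in sections 7.3 and 10.1.1.2. The schedule starts at first onset, so it is not reserved for severe cases.

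What is at stake is the dose given to a small child at a site that follows the page. No DLT count, decision rule or statistical result depends on it.

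**Working it through.** **Is loperamide out of line with the rest of the protocol?** Every supportive drug with a printed dose was listed with its dosing unit.

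| Drug | Where | Unit |
|---|---|---|
| Acetaminophen | Tables 5–7, 6.2.1.4, 7.2.1 | mg/kg, capped |
| Diphenhydramine | Tables 5–7, 6.2.1.4, 7.2.1 | mg/kg, capped |
| Hydroxyzine | Footnotes to Tables 5–7 | mg/kg, capped |
| Ibuprofen | 6.2.1.4 | mg/kg |
| Morphine | 6.2.1.4 | mcg/kg |
| Gabapentin | 6.2.1.4 | mg/kg, capped |
| Lidocaine | 6.2.1.4 | mg/kg/hour |
| Epinephrine | 7.2.1 | mg/kg, capped |
| Methylprednisolone | 7.2.1, 7.2.6 | mg/kg |
| Dexamethasone | 7.2.1 | mg/kg |
| Prednisone | 7.2.6 | mg/kg/day |
| Hydrocortisone | 3.2.10, 6.7, 7.3.2.2 | mg/kg |
| **Loperamide** | **7.1** | **fixed mg** |

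Twelve of the thirteen are per kg, and loperamide is the exception. Drugs named without a dose (fentanyl, hydromorphone, albuterol, infliximab and others) are left out. Saline boluses are a fluid and not counted, but they too are per kg (7.3.2.1). The study agents are also scaled to body size, magrolimab per kg and dinutuximab per m², and section 8.1.1 sets magrolimab infusion volumes by age group.

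**How far does the dose vary per kg?** Inputs from section 7.1: first dose 4 mg, repeat 2 mg, ceiling 16 mg in 24 hours. Body weights are assumptions, because the documents give none: 10–15 kg for the youngest patients and 70 kg for an adult. The formula is dose ÷ weight.

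| | 10 kg | 15 kg | 70 kg |
|---|---|---|---|
| First dose, 4 mg | 4/10 = 0.40 | 4/15 = 0.27 | 4/70 = 0.06 |
| First dose plus one repeat, 6 mg | 6/10 = 0.60 | 6/15 = 0.40 | 6/70 = 0.09 |
| Ceiling in 24 h, 16 mg | 16/10 = 1.60 | 16/15 = 1.07 | 16/70 = 0.23 |

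All results are in mg/kg. The ratio to the adult figure is the inverse weight ratio: 70/15 = 4.7 to 70/10 = 7.0.

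**What does the ceiling represent?** Repeats needed to reach it: (16 − 4)/2 = 6. A patient therefore gets there only with the first dose and six more within 24 hours. The first-dose row applies to every patient treated as printed; the ceiling row is a bound and not expected exposure.

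**Does any other text override the printed dose?**

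- The standard-practice sentence is general. The same introduction then directs the reader to the event-specific tables, where this schedule is the specific instruction.
- The consultation sentence follows the text on Grade 3 events, so its reach to milder diarrhea is unclear, and it supplies no dose.
- The Investigator's Brochure reference sits in 7.2, not 7.1, and the Brochure is not among the documents.

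None of the three gives a pediatric loperamide dose or limits the printed schedule to larger patients.

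**The case against.** The best counter-argument is that section 7 already protects children. Its standard-practice sentence is a requirement, whereas the loperamide schedule is only recommended. On that reading the requirement governs, and a pediatric team would dose a 2-year-old by its own practice. The consultation sentence states no grade limit of its own and could add a further check. This reading is possible, and it limits how often the printed dose would actually be given. It does not settle the matter, because a site looking up diarrhea finds a specific milligram dose and ceiling with no sign that they are meant for larger patients.

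The second argument is that harm is not shown. The documents contain no pediatric loperamide limit, so a fixed dose is not thereby a toxic one. Any fixed dose divided by a smaller weight gives a larger mg/kg figure, so the 4.7- to 7-fold ratio says nothing particular about loperamide, and the weights behind it are assumed. All of this stands. The mg/kg figures are illustrative, and no rate of diarrhea by age or grade, nor any number of affected patients, can be derived.

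What remains is an inconsistency with the protocol's own dosing convention, in a line that could be applied to very small children. That supports a low-priority correction and nothing stronger.

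**Conclusion.** The point holds, at the lowest level of severity. Confidence is high that the schedule is fixed, unqualified and the only one of thirteen printed supportive drug doses not scaled to weight, in a trial open from age 2. That comparison rests on the protocol alone.

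The size of the discrepancy depends on the assumed 10–15 kg and 70 kg; at those weights the youngest patients' dose per kg, if the line is followed as printed, is about 5 to 7 times the adult's. It is not claimed that the dose is toxic, that sites would fail to adjust it, or that any design quantity or analysis changes.

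**What to change.** In the diarrhea table of section 7.1, do one of two things:

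- replace the schedule with an age- or weight-based loperamide dose and daily maximum, set by the clinical and pharmacy team; or
- delete the schedule and refer to institutional guidelines, in line with section 6.2.1.4 and with the dose-free nausea and vomiting tables beside it.

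No dose is proposed here, because the documents offer no basis for one. The cost is one line of wording, which can go into the next amendment, and a pharmacy check.

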# 7.2 Hu5F9-G4 (Magrolimab) AE Management and Dose Interruption Guidelines

For detailed information regarding management of AEs associated with Hu5F9-G4 (magrolimab), please refer to the most current version of the Hu5F9-G4 (magrolimab) Investigator's Brochure.

# **7.2.1** Management of Infusion-related Reactions (IRR)

The most common adverse events associated with IRRs include chills, pyrexia, back pain, nausea, vomiting, hypotension, dyspnea, and headache. These primarily occur with the first two doses of Hu5F9-G4 (magrolimab), and are mostly observed during the infusion or several hours afterward.

#### **Preventive Measures**

Premedication should include oral acetaminophen and an antihistamine (IV or oral) before the first two doses of Hu5F9-G4 (magrolimab) or in case of re-priming of Hu5F9-G4 (magrolimab), please refer to Table 5.

Recommendations for the management of IRRs are provided below.

Toxicity	Severity	Management
Infusion-related Reactions	Grade 1 – mild transient reaction	Remain at bedside and monitor patient until recovery from symptoms.
	Grade 2 - infusion interruption is indicated, but patient responds promptly to symptomatic treatment (e.g.,	Stop the Hu5F9-G4 (magrolimab) infusion, begin an intravenous (IV) infusion of normal saline, and consider treating the patient with diphenhydramine (0.5 – 1 mg/kg, max 50 mg) IV (or equivalent) and/or 10 mg/kg, max dose 650 mg oral acetaminophen.  Remain at bedside and monitor patient until resolution of symptoms.
	antihistamines, non-steroidal	Corticosteroid therapy may also be given at the discretion of the Investigator.
	anti-inflammatory drugs, narcotics, corticosteroids,	If the infusion is interrupted, wait until symptoms resolve, then restart the infusion at 50% of the original infusion rate.
	IV fluids); and prophylactic medications are	If no further complications occur after 1 hour ( $\pm$ 10 minutes), the rate may be increased to 100% of the original infusion rate. Monitor the patient closely.
	indicated for ≤24 hours	If symptoms recur, stop infusion and disconnect patient from the infusion apparatus. No further Hu5F9-G4 (magrolimab) will be

Toxicity	Severity	Management
		administered at that visit.
		Premedications should be considered before any future infusions.
		The amount of Hu5F9-G4 (magrolimab) infused must be recorded on the case report form (eCRF).
		Patients who experience a grade 2 IRR during the post-infusion observation period that does not resolve during that time should be observed until the AE resolves, with vital sign measurements as medically indicated for the management of the AE.
	Grade 3 -	Immediately discontinue infusion of Hu5F9-G4 (magrolimab).
	prolonged infusion related reactions (e.g., not rapidly responsive to symptomatic medication and/or brief interruption	Begin an IV infusion of normal saline, and consider treating the patient as follows: Administer bronchodilators, epinephrine 0.01 mg/kg up to 0.5 mg of a 1:1,000 solution for subcutaneous administration or 0.01 mg/kg of a 1:10,000 solution injected slowly for IV administration and/or diphenhydramine 0.5 – 1 mg/kg IV with methylprednisolone 1 mg/kg IV (or equivalent), as needed.
	of infusion), or recurrence of	The patient should be monitored until the Investigator is comfortable that the symptoms will not recur.
	symptoms following initial improvement, or where	Patients who have grade 4 IRRs occurring with the first dose (priming dose) will be permanently discontinued from study treatment.
	hospitalization is indicated for other clinical sequelae (e.g., renal impairment, pulmonary infiltrates)	Patients who experience grade 3 IRRs must be given premedication prior to all subsequent doses. In this setting, premedication with oral acetaminophen (10 mg/kg, max dose 650 mg), oral or IV diphenhydramine (0.5 – 1 mg/kg, max dose 50 mg), and IV dexamethasone (0.6 mg/kg), or a comparable regimen, is recommended for the subsequent 2 doses. Continued premedication with corticosteroids beyond these 2 doses may be administered at the discretion of the treating physician.
	or Grade 4 - having life-threatening	Patients who receive premedication with a corticosteroid and still experience a grade 3 or 4 infusion-related reaction will be permanently discontinued from study treatment.
	consequences and where urgent	Investigators should follow their institutional guidelines for the treatment of anaphylaxis.
	intervention indicated)	All patients with grade 3 or greater IRRs will be observed until the AE(s) resolves or stabilizes, with vital sign measurements and additional evaluations, as medically indicated for the management of the AE(s).

In the case of late-occurring hypersensitivity symptoms (e.g., appearance of localized or generalized pruritus after Day 1 but within 1 week after treatment), symptomatic treatment may be given (e.g., oral antihistamine or corticosteroids).

### 7.2.2 Magrolimab Dosing Guidance for Planned Surgical Procedures

Surgical Procedure	Magrolimab Dose Guidance	
Minimally invasive procedure  (Examples: biopsies (excluding lung/liver), skin/subcutaneous lesion removal, cataract/glaucoma/eye surgery, cystoscopy)	Hold magrolimab dose 3 days prior to procedure and restart 3 days after.	
Moderately invasive procedure  (Examples: lung/liver biopsy, hysterectomy, cholecystectomy, hip/knee replacement, minor laparoscopic procedures, stent/angioplasty)	Hold magrolimab dose 5 days prior to procedure and restart 5 days after.	
Highly invasive procedure  (Examples: CNS/spine surgery, major vascular surgery, cardiothoracic surgery, major laparoscopic surgery)	Hold magrolimab dose 7 days prior to procedure and restart 7 days after.	

# 7.2.3 Hemagglutination and Microangiopathy

In the phase 1 trial experience with Hu5F9-G4 (magrolimab) in solid tumors and AML, agglutination of RBCs has been observed on peripheral smear. Hu5F9-G4-related microangiopathy is a possible sequela of hemagglutination; however, it has not been observed in the ongoing phase 1 clinical trials to date. In addition, AEs may be associated with findings of hemagglutination. Monitoring of hemagglutination and microangiopathy includes physical exam assessments, complete blood counts (CBCs), and serum chemistries testing as outlined in the schedule of assessments (SOA).

### **7.2.4** Anemia, Blood Cross-Matching, and Red Blood Cell Transfusion Procedures

Hemoglobin level must be documented as detailed in section 6.2.1.3. Patients with a low baseline hemoglobin level, especially those with cardiac history or risk factors, must be monitored closely after initial administrations of Hu5F9-G4 (magrolimab) as preexisting anemia can be exacerbated.

Hu5F9-G4 (magrolimab) binds to red cells and leads to erythrophagocytosis. This, coupled with anemia from other causes in patients with cancers, means that care must be taken with RBC cross-matching and packed red blood cell (PRBC) transfusions. There is a possibility that treatment with Hu5F9-G4 (magrolimab) may obscure assessment of RBC phenotyping.

 During the Screening Period prior to initiation of Hu5F9-G4 (magrolimab) therapy, blood cell ABO phenotyping for minor antigens, type and screen (ABO/Rh), and Direct Antiglobulin Test (DAT) will be performed for each patient. This, together with using the prior phenotype, will facilitate allocation of properly cross-matched blood, should a blood transfusion be warranted.

# Before Exposure to Hu5F9-G4 (magrolimab)

In participants who have not been transfused in the preceding 3 months, an extended RBC phenotyping including minor antigens (Rh CcDEe, Cw, MNSs, K [k if K+] Fya, Fyb, Jka, and Jkb) should be performed at screening. In these participants, blood genotyping (that includes minor antigens Rh CcDEe, Cw, MNSs, K [k if K+] Fya, Fyb, Jka, and Jkb) is acceptable as an alternative to extended phenotyping.

Because transfused blood can interfere with RBC phenotyping assessment, participants who received blood transfusion in the preceding 3 months should have their blood genotype documented at screening, and for these participants extended RBC phenotyping is not sufficient and does not need to be performed.

# Results should be available before the first dose of magrolimab.

# Procedure for patients after exposure to Hu5F9-G4 (magrolimab)

In case ABO/Rh type cannot be resolved, use pretreatment phenotype/genotype matched units for ABO, Rh and other minor RBC antigens (CcDEe and Kk, to the feasible extent).

